**Baseline definition:**

Baseline of each parameter is defined as the latest value on or prior to the first DOXIL or trabectedin infusion in cycle 1.

In addition to the cycle day and study day defined above, the laboratory assessments completed on Day 1 of a cycle are considered to be baseline for that cycle as well as the last laboratory assessment for the previous cycle.

**2.1.2. Pooling Strategy for Analysis Centers**

Treatment-by-center interaction will not be formally tested. It can be assessed by graphics with regions/countries ordered according to their size.

**2.1.3. Analysis Sets**

“All Randomized Subjects” analysis set is defined as all subjects who are randomized to this study, independent of whether they received study drug or not.

“All Treated Subjects” analysis set is defined as all randomized subjects who receive at least 1 dose of DOXIL or trabectedin. Subjects who receive dexamethasone (or an equivalent corticosteroid) as pre-medication but who do not receive DOXIL or trabectedin will not be included in “All Treated Subject” analysis set.

The PK analysis set is defined as all subjects who received at least 1 dose of trabectedin and had at least 1 PK measurement.

YONDELIS®: Statistical Analysis Plan Study ET743-OVC-3006

### **2.1.3.1. Efficacy Analysis Sets**

The “All Randomized Subjects” analysis set will be used.

### **2.1.3.2. Safety Analysis Set**

The safety analysis is based on the “All Treated Subject” analysis set, where the grouping into the different arms is based on the true treatment received during the first cycle.

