## **6. DOSAGE AND ADMINISTRATION**

Janssen Research & Development (JR&D) will provide trabectedin and DOXIL as IV formulations. The amount (in mg) of trabectedin and DOXIL to be administered will be determined by subject body surface area (BSA), which will be calculated according to the standard nomogram used at each center. Body surface area will be calculated either at Screening or on Day 1 of Cycle 1. It will not be necessary to recalculate BSA at each cycle unless the institution requires it or the subject has a significant weight change (approximately >10%). For those subjects with a body mass index (BMI)  $\geq 30$ , the use of ideal body weight for dose calculation and capping of BSA utilized for dosing calculations will be left to the discretion of the investigator and to institutional guidelines. The calculated dose of DOXIL may be rounded to the nearest full mg that can be administered accurately. The dose of trabectedin may be rounded to the nearest second decimal place (eg, 1.721 can be rounded to 1.72) that can be administered accurately. The first dose of study drug may be administered at any time within 7 days of randomization. This period is to allow for the placement of central venous access, if a subject is assigned to the trabectedin+DOXIL arm of the study.

**Treatment Arm A:** DOXIL 30 mg/m^2 administered as an IV infusion over approximately 90 minutes (per package insert) followed by trabectedin 1.1 mg/m^2 administered as an IV infusion over approximately 3h, via central venous access, every 3 weeks. Central venous access is required for administration of trabectedin. If no infusion-related reaction is observed with DOXIL after the first infusion, DOXIL may be administered as a 60- to 90-minute infusion in subsequent cycles.

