All subjects assigned to Treatment Arm A will be premedicated with 20 mg dexamethasone, administered IV approximately 30 minutes before the start of the DOXIL infusion, to reduce the incidence of transaminase elevation related to trabectedin. If dexamethasone is not available, an equivalent IV dose of another corticosteroid may be substituted. For subjects in Treatment Arm A, trabectedin will be administered as an IV infusion over approximately 3h immediately after the catheter is flushed well with 5% dextrose in water (D5W). Trabectedin should be diluted in normal saline or D5W to a volume of at least 500 mL and infused via a central venous catheter. Any calibrated infusion pump may be used to deliver the drug. The administration of both drugs will be repeated every 3 weeks. The prophylactic use of granulocyte-colony stimulating factor (G-CSF) is strongly recommended for those subjects assigned to Treatment Arm A.

**Treatment Arm B:** DOXIL, 50 mg/m^2 administered as an IV infusion over approximately 90 minutes (per package insert) every 4 weeks. If no infusion-related reaction is observed with DOXIL after the first infusion, DOXIL may be administered as a 60- to 90-minute infusion in subsequent cycles. DOXIL may be administered through a central or peripheral venous catheter.

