### **11.7. Safety Analyses**

All subjects who have received at least part of 1 dose of study drug will be included in the safety analysis, according to the actual treatment received. The safety parameters to be evaluated are the incidence, intensity, and type of adverse events, ECGs, LVEF assessments (MUGA scans or 2D-ECHOs), and clinical laboratory results. Exposure to the study drugs and reasons for discontinuation of study treatment will be tabulated.

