## 2. ANALYSES PLANNED

### 2.1. General Analysis Definitions

#### 2.1.1. Definition of Cycle, Treatment Phase, Baseline

**Cycle:** The duration of cycles may not consistently be as the planned 21 days in the trabectedin + DOXIL Arm or 28 days in the DOXIL Arm, it will depend on the earliest date of the DOXIL/trabectedin doses given in the next cycle. If a subject experiences toxicity at the planned start of a cycle that leads to a delay in DOXIL/trabectedin administration, this new cycle will be delayed, and the previous cycle will be prolonged (without additional DOXIL or trabectedin treatment).

The start of the cycle is the date of the first administration of DOXIL or trabectedin in a cycle. The end of a cycle is the day before the first infusion of the immediate subsequent cycle recorded on the case report form (CRF).

The last cycle ends 3 weeks after the start of this cycle for the trabectedin + DOXIL Arm, and 4 weeks for the DOXIL Arm.

The assessments performed during the 'End-of-treatment visit' will be included in the last treated cycle for analysis.

All lab samples taken after the last treatment and up to 30 days after the last DOXIL/trabectedin infusion will be captured in the last cycle.

**End-of-treatment phase:** The end of the treatment phase is the date the last cycle ends, i.e., 3 weeks after the first trabectedin or DOXIL dosing in the last cycle for Arm A, or 4 weeks after the dose of DOXIL in the last cycle for Arm B.

YONDELIS®: Statistical Analysis Plan Study ET743-OVC-3006

**Follow-up phase:** Following termination of DOXIL/trabectedin treatment, subjects are followed every 8 weeks for survival for the first 2 years after randomization and every 3 months thereafter until death or the clinical cut-off date defined at the time when 514 deaths are observed, whichever is sooner. If disease progression has not occurred at treatment termination, then disease assessment should continue every 8 weeks until there is evidence of disease progression or death, or until the clinical data cut-off date, or until the start of first subsequent therapy for ovarian cancer, whichever is earlier. Disease assessment will also be done if necessary to confirm response or document disease progression.

**Relative day:** Assessments will be presented chronologically by cycle day or study day, which are defined in the following:

Cycle day = assessment date - date of first DOXIL or trabectedin infusion for the cycle + 1

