#### **2.2.9. Safety**

##### **2.2.9.1. Adverse Events**

Treatment emergent adverse events will be summarized by disease group and overall. A treatment-emergent adverse event is defined as any AE occurring or worsening on or after the first treatment of DOXIL/Trabectedin, and within 30 days after the last dose. For imputation rules for incomplete dates, see Attachment 4.1.

Adverse events are documented on the CRF together with their severity, according to the NCI CTC version 4.0, also referred to as NCI toxicity grading. For the categorization of the adverse events, the MedDRA dictionary will be used. Adverse events are considered drug related when the relation to trial medication is considered to be possible, probable, or very likely, according to the investigator's opinion.

Summary of overall adverse events will be done by body system and preferred term, by severity (worst toxicity grade), by relationship to the study drugs (trabectedin or DOXIL), and by AE outcome. Tables will be sorted by body system/preferred term and by the highest incidence. In the AE database, "neoplasm malignant aggravated", and "condition aggravated" are created terms to match the Global Medical Safety (GMS) death reporting database (in case of death due to disease progression). These will not be included in the AE summaries.

A listing will be prepared on all adverse events. If data is available, a listing for delayed adverse events (defined as new onset of AE occurring 30 days after last dose as judged by investigator to be related to trial medication) will be presented.

YONDELIS®: Statistical Analysis Plan Study ET743-OVC-3006

First occurrence of grade 3 and 4 adverse events will be reported by cycle. The drug related grade 3 and 4 adverse events would be summarized.

A frequency table will be made for the AEs leading to cycle delay, dose reduction, skipped dose, or withdrawal of study medication. Adverse events leading to permanent stop and AE with outcome death will also be presented by drug relatedness.

For all serious adverse events (SAEs), the investigator has to send an SAE form to the Janssen R&D GMS. The AEs that are indicated on the CRF as serious are used for the summary tables. A summary table by any grade SAEs will be presented. A similar table will be presented for the drug-related SAEs.

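### The SAP's first-cycle grouping rule, read literally, puts an Arm A subject who first receives trabectedin in cycle 2 into the DOXIL arm of the safety tables

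*SAP*

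**What the plan says.** SAP 2.1.3.2 bases safety on the All Treated set and adds that "the grouping into the different arms is based on the true treatment received during the first cycle". SAP 2.1.3 defines that set as "all randomized subjects who receive at least 1 dose of DOXIL or trabectedin", so a subject given DOXIL alone qualifies. In Protocol 11.7, subjects with at least part of one dose "will be included in the safety analysis, according to the actual treatment received"; the first cycle is not mentioned.

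Two other provisions bear on the rule. SAP 2.1.1 lets either drug open a cycle: "The start of the cycle is the date of the first administration of DOXIL or trabectedin in a cycle". SAP 2.2.9.1 counts an adverse event as treatment-emergent from the first dose of either drug to 30 days after the last dose, so events from all later cycles go wherever the subject was placed at cycle 1.

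**The concern.** The Arm A regimen is two infusions in sequence. DOXIL comes first; then, under Protocol 6, "trabectedin will be administered as an IV infusion over approximately 3h immediately after the catheter is flushed well with 5% dextrose in water". The same section adds: "Central venous access is required for administration of trabectedin". A first cycle in which DOXIL is given and trabectedin is not is therefore possible. For that subject, the literal answer to what she received in cycle 1 is DOXIL.

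If she then receives trabectedin from cycle 2, its hepatic and haematologic toxicity is reported in the control column. Arm B contains no trabectedin, so the opposite shift needs a treatment error. At stake is how accurately the clinical study report shows the toxicity difference between arms, above all for events that are rare on DOXIL alone.

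**Working it through.** The plan states no figure on this point, so there is nothing to reproduce. The check is a reading of the text, followed by an illustration of scale.

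**Can the case arise, and where does the rule put it?**

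1. DOXIL alone in cycle 1 puts the subject in the All Treated set (SAP 2.1.3) and starts her cycle 1 (SAP 2.1.1).
2. Omitted doses are foreseen. SAP 2.2.9.1 plans a table of "AEs leading to cycle delay, dose reduction, skipped dose, or withdrawal of study medication". Protocol 6.2.2 also provides for Arm A subjects treated with one of the two drugs.
3. Neither document describes trabectedin first given in cycle 2, but neither rules it out.
4. SAP 2.1.3.2 makes no exception for an incomplete first cycle and does not address trabectedin first given later. Nothing elsewhere overrides it.
5. The adverse event window then carries her later events into the arm assigned at cycle 1.

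The affected group is narrow. Under SAP 2.1.1, cycle 1 runs until the day before the next cycle's first infusion, so trabectedin given late within cycle 1 still counts. Protocol 11.7 counts part of a dose, so a partial trabectedin infusion arguably counts too. What remains is no trabectedin at all in cycle 1, then trabectedin later.

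**Scale (illustration only).** Inputs:

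- Planned subjects per arm: n = 335 (SAP 1.2). This is the planned number, not the number treated.
- Grade 3 or 4 event rates in the earlier phase 3 study (Protocol 1.2.2): ALT 32% on the combination and 1% on DOXIL; neutropenia 63% and 23%.
- Misgrouped subjects: k = 1 to 17 (0.3% to 5.1% of 335). This is an assumption, because the documents give no count.

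Let pA and pB be the combination and DOXIL rates. If the k subjects carry rate pA, the Arm A rate is unchanged and the observed DOXIL-arm rate is (335 × pB + k × pA) / (335 + k). For ALT with k = 3: (3.35 + 0.96) / 338 = 1.28%, and the ratio is 32 / 1.28 = 25.

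| k | DOXIL-arm ALT | ALT ratio (32 without misgrouping) | ALT difference (31.0 points without misgrouping) | DOXIL-arm neutropenia (23.0% without misgrouping) |
|---|---|---|---|---|
| 1 | 1.09% | 29.3 | 30.91 | 23.12% |
| 3 | 1.28% | 25.1 | 30.72 | 23.36% |
| 7 | 1.63% | 19.6 | 30.37 | 23.82% |
| 10 | 1.90% | 16.9 | 30.10 | 24.16% |
| 17 | 2.50% | 12.8 | 29.50 | 24.93% |

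Even at k = 17 the absolute differences shrink by no more than about 2 points (ALT 1.5, neutropenia 1.9). The ratio moves visibly only for the event that is rare on DOXIL.

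**Direction for Arm A subjects who never receive trabectedin.** Suppose 3 such subjects carry the DOXIL ALT rate of 1%. Kept in Arm A, they give (332 × 0.32 + 3 × 0.01) / 335 = 31.72% against 1.0%, a difference of 30.72 points. Moved out, the arms show 32.0% against 1.0%, a difference of 31.0 points. Here the rule makes the combination look slightly worse. If instead such a subject stopped because of a serious early reaction, moving her takes that event out of Arm A. The sign depends on which kind of subject is involved.

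**The case against.** The strongest reply is that true treatment means the regimen. Arm B is DOXIL 50 mg/m² every 4 weeks. An Arm A subject given 30 mg/m² after dexamethasone has not received Arm B's treatment, so a programmer could properly keep her in Arm A and use the rule only to correct wrong-arm treatment. That reading is open. The SAP does not choose it, however, and the literal reading is equally available. The two give different tables, so the text needs settling even though no actual misassignment has been shown.

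The SAP also offers partial safeguards. Events are summarised by relationship to each drug and all are listed (2.2.9.1), and interrupted infusions are listed with reasons (2.2.5). These would help a reader trace a case, but they do not change the arm columns, and a list of interrupted infusions need not show an infusion that was never started. Anchoring on cycle 1 also has a sound purpose: a combination subject who later continues on one drug stays in Arm A. The fix keeps that.

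A reader might infer more than the documents support:

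- **That the rule biases the whole safety comparison in favour of the combination.** It does not follow. For subjects who never receive trabectedin, the direction can go either way, as the working shows.
- **That adverse event deaths could shift materially.** The earlier study had 5 such deaths (2%) on the combination and 2 (1%) on DOXIL. Moving one gives 4 against 3, but that presupposes that a misgrouped subject is one of the deaths. At a 2% rate, 3 misgrouped subjects carry 3 × 0.02 = 0.06 expected deaths.
- **That the rule casts doubt on the decision to stop.** The monitoring committee reviewed toxicity on 15 December 2017. SAP 2.2 sets the report's analysis at the 18 January 2018 cutoff. Nothing shows that this grouping affected the committee's review.

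**Conclusion.** The point holds in a limited form. SAP 2.1.3.2 is narrower than Protocol 11.7. Read literally, it allows trabectedin toxicity to be tabulated under DOXIL for an Arm A subject whose trabectedin begins after cycle 1. For that subject the shift runs toward a smaller difference between arms.

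The effect is probably very small and matters mainly for events rare on DOXIL alone. This rests on an assumed number of misgrouped subjects, the planned arm size, and event rates borrowed from the earlier study. For Arm A subjects who never receive trabectedin, the documents do not determine the direction of any bias. This is a cheap improvement to an unclear definition, not a flaw that threatens the trial's conclusions.

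**What to change.** Replace the first-cycle rule in SAP 2.1.3.2 with the following text:

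*Treated subjects are analysed by actual treatment received over the whole treatment phase. Any subject who received any trabectedin, including a partial infusion, is analysed in the trabectedin + DOXIL arm. A subject randomised to Arm A who received only the Arm A DOXIL component remains in Arm A. A subject randomised to Arm A is grouped in the DOXIL arm only if she was given the Arm B regimen.*

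Add a listing of subjects with an incomplete first cycle and of any Arm B subject given trabectedin in error. This brings the SAP into line with Protocol 11.7 and settles how partial doses and later trabectedin are treated. The cost is one extra derivation and one listing. No new data are needed.

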### **2.1.3.3. Definition of Subgroup**

In addition to the main analysis, the efficacy analysis will be performed by the levels of stratification factors.

## **2.2. Methods of Analysis**

Final efficacy and safety analysis for the CSR will be using clinical cut-off date of January 18, 2018.

### **2.2.1. Statistical Hypotheses for Trial Objectives**

Overall Survival (OS) will be compared between treatment arms using an unstratified one-sided log-rank test. The trabectedin + DOXIL combination therapy will be declared better than DOXIL monotherapy if the OS is better with a p-value less than or equal to the significance level as specified by the alpha spending function. The overall 2-tailed significance level of 0.05 will be spread over 1 interim and 1 final OS analyses, when approximately 308 and 514 events on OS (death) are seen.

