#### *Primary Endpoint*

Overall survival is defined as the time between the date of randomization and the date of death. Subjects who die, regardless of the cause of death, will be considered to have had an event. Subjects who are still being treated, who are lost to follow-up prior to the end of the study, or who have withdrawn consent from the study will be censored at the last available date where the subject is known to be alive.

Overall survival will be compared between both treatment arms by the un-stratified, 2-sided, log-rank test. The analysis of the primary endpoint, OS, will be conducted after at least 514 events (deaths) are observed or until the clinical cutoff date. An interim analysis is planned for this study; after observing 60% (308 death events) of the total number of required (514) death events. The Kaplan-Meier method will be used to estimate the distribution of functions of OS for each treatment arm. The number of events, subjects censored, the estimate of medians, and 95% CI for the medians will be presented. Survival rates will be calculated using the Kaplan-Meier method. The un-stratified Cox proportional hazards model will be used to obtain the HR and its 95% CI.

Overall survival will also be compared between the treatment arms by a 2-sided log-rank test, stratified for: the time from the last dose of first-line platinum therapy to disease progression (6 months to 12 months vs >12 months to 24 months vs >24 months), ECOG performance status grade (0 vs 1), BRCA 1/2 status (mutation vs no mutation), and prior DOXIL therapy (no vs yes).

In case an imbalance in baseline prognostic factors is observed, especially PFI, a Cox proportional hazards model will also be used to compare the 2 treatment arms. The following baseline information includes as covariates: baseline ECOG (0 vs 1), PFI (as continuous), BRCA 1/2 status (mutation vs no mutation), prior DOXIL therapy (no vs yes), and any imbalanced factors. From the Cox proportional hazards regression, HR estimates and their 95% CIs will be estimated for treatment and for the prognostic factors.

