#### **11.8. Interim Analysis**

One interim analysis is planned for this study after observing 60% (308 events) of the total number of required (514) events (deaths). The  $\alpha$  spent will be 0.008 for the interim analysis. The O'Brien-Fleming boundaries as implemented by Lan-DeMets  $\alpha$ -spending functions are used for the boundary. The  $\alpha$  spent will be adjusted accordingly based on the actual number of events observed. Operating characteristics for the boundaries are presented in [Table 6](#).

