### 1.3. Sample Size Justification

It is assumed that failure will follow an exponential distribution with a constant hazard rate. Assuming a median OS of 16 months for the active control group (DOXIL monotherapy), a planned sample size of approximately 670 subjects will provide 80% power to detect a HR of 0.78 (16 months versus 20.5 months; corresponding to a 28% improvement in median OS) at a 2-tailed significance level of 0.05 and an enrollment duration of approximately 52 months (13 subjects/month enrollment) over a total study duration of 64 months to obtain the required 514 events.

The OS endpoint will incorporate group sequential design by including 1 interim analysis and 1 final analysis using the O'Brien-Fleming boundaries as implemented by the Lan-DeMets alpha spending method. Subjects will be randomized in a 1:1 ratio to receive trabectedin + DOXIL combination therapy or DOXIL monotherapy.

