### **2.2.8. Efficacy**

#### **2.2.8.1. Analysis Specifications**

##### **2.2.8.1.1 Level of Significance**

For the primary endpoint OS, the overall (two-sided) significance level is 0.05. This 0.05 will be spread over 2 analyses by an O'Brien-Fleming boundaries as implemented by Lan-DeMets alpha spending function. The significance of efficacy will be claimed if the p-value is less than or equal to the significance level as calculated based on the above specified alpha spending function and the observed number of events.

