**2.2.8.2. Primary Endpoint: Overall Survival**

*Overall survival* (OS) is defined as the time between the randomization and death. Subjects who die, regardless of the cause of death, will be considered to have had an event. All subjects who are lost to the follow-up prior to the end of the trial or who are withdrawn from the trial will be censored at the time of last contact. Subjects who are still being treated will be censored at the last available date where the subject is known to be alive.

OS will be compared between treatment arms using an unstratified two-sided log-rank test as primary analysis. The Kaplan-Meier method will be used to estimate the distribution functions of OS for each treatment arm. The number of events, subjects censored, the estimate of medians and 95% confidence interval for the medians will be presented. The plots of OS using the Kaplan-Meier method will be presented.

Six-month and one-year survival rates will be calculated using the Kaplan-Meier method. The unstratified Cox proportional hazards model will be used to obtain the HR and its 95% CI.

OS will also be compared between treatment arms by a two-sided log-rank test, stratified for the stratification factors: the time from the last dose of first-line platinum therapy to disease progression (6 to 12 months vs >12 to 24 months vs >24 months), Eastern Cooperative Oncology Group (ECOG) performance status score (0 vs 1), BRCA 1/2 status (mutation vs. no mutation) and prior pegylated liposomal doxorubicin therapy (no vs yes).

In case an imbalance in baseline prognostic factors is observed, especially PFI (platinum-free interval: the time from the last dose of first-line platinum therapy to disease progression), a Cox proportional hazards model will also be used to compare 2 treatment arms. The following baseline information includes as covariates: baseline ECOG ("0" vs. "1"), PFI (as continuous), BRCA1/2 status (mutation vs. no mutation), prior pegylated liposomal doxorubicin therapy (no vs yes), and any imbalanced factors. From the Cox proportional hazards regression, HR estimates and their 95% CIs will be estimated for treatment and for the prognostic factors.

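### The OS success rule in SAP 2.2.1 sets a one-sided log-rank p-value against levels from a 2-tailed 0.05 without halving them, contradicting the two-sided primary test in SAP 2.2.8.2 and Protocol 11.3.

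*SAP*

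**What the plan says.** SAP 2.2.1, the section on statistical hypotheses, says when the combination will be declared better on OS. The test is given as: "Overall Survival (OS) will be compared between treatment arms using an unstratified one-sided log-rank test". The p-value must not exceed the level set by the alpha spending function, and the same paragraph gives the source of that level: "The overall 2-tailed significance level of 0.05 will be spread over 1 interim and 1 final OS analyses".

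The other places that describe the OS test or its level are two-sided:

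- SAP 2.2.8.2: "OS will be compared between treatment arms using an unstratified two-sided log-rank test as primary analysis".
- Protocol 11.3, Primary Endpoint: "Overall survival will be compared between both treatment arms by the un-stratified, 2-sided, log-rank test".
- SAP 2.2.8.1.1: "For the primary endpoint OS, the overall (two-sided) significance level is 0.05". This section also has a rule for claiming efficacy, with the level "as calculated based on the above specified alpha spending function and the observed number of events".
- SAP 1.3 sizes the trial "at a 2-tailed significance level of 0.05 and an enrollment duration of approximately 52 months".

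The table in SAP 2.2.2.2 gives efficacy boundaries of HR 0.74 at 308 deaths and 0.84 at 514, with cumulative alpha of 0.008 and 0.050. SAP 2.2.2.2 then records that the second futility analysis gave HR 0.962 against a threshold of 0.93, and that the planned interim will not be done. SAP 2.2 still schedules the final efficacy analysis at the 18 January 2018 cutoff.

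**The concern.** The SAP names two different tests for the same primary endpoint, and one of them is in the paragraph that defines success. A one-sided test is sound if its p-value is set against a one-sided level. SAP 2.2.1 instead points to levels that come from a two-tailed 0.05, and neither document says to halve them. Followed to the letter, that rule would nearly double the chance of declaring the combination better when it is not.

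The SAP marks hierarchical testing, OS subgroups and patient-reported outcomes as not to be performed. It puts no such note on SAP 2.2.1 or on the OS log-rank test. An OS p-value is therefore still due, under two conflicting instructions, and the two p-values differ by a factor of two.

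**Working it through.** **Inputs.** HR 0.78, 80% power, 514 deaths, 1:1 allocation (SAP 1.3); looks at 308 and 514 deaths with O'Brien-Fleming boundaries by Lan-DeMets spending (SAP 2.2.2.2); observed HR 0.962 (SAP 2.2.2.2); 232 deaths at the second futility look (SAP 2.2.2.1).

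**1. Sample size.** Freedman's formula is d = [(1+HR)/(1−HR)]² × (z_α + z_β)².

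- Two-sided 0.05: (1.78/0.22)² × (1.960 + 0.842)² gives 514 deaths, the SAP's figure. Schoenfeld's formula gives 509.
- One-sided 0.05: 405 deaths (Schoenfeld 401).

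The sizing is two-sided 0.05.

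**2. Planned boundaries.** The information fraction is t = 308/514 = 0.599. The spend per side is 2[1 − Φ(z₀.₀₁₂₅/√t)] = 0.003785, or 0.00757 over both sides. The boundary on the HR scale is exp(−2z/√d). The final z is solved from the bivariate normal with correlation √t.

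| Rule | Interim z | Final z | HR at 308 | HR at 514 | Chance of falsely favouring the combination | Power at HR 0.78 |
|---|---|---|---|---|---|---|
| Two-sided 0.05 (same as one-sided 0.025, half the spend) | 2.671 | 1.981 | 0.738 | 0.840 | 2.5% | 80.1% |
| SAP 2.2.1 read literally: one-sided p against 0.00757, then 0.0476 | 2.429 | 1.668 | 0.758 | 0.863 | 4.95% | 87.6% |
| One-sided 0.05 with its own spending (interim 0.0113) | 2.279 | 1.679 | 0.771 | 0.862 | 5% | 87.5% |

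The first row reproduces the SAP table: 0.00757 rounds to 0.008, the final nominal two-sided level of 0.0476 rounds to 0.048, and the boundaries round to 0.74 and 0.84. The other two rows do not.

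**3. Analysis at the cutoff.** The documents do not give the death count, so a range is assumed. The lower end is 232. For the upper end, the SAP's planned rate is (514 − 308)/(64 − 43) = 9.8 deaths per month. From 20 September 2017 to 18 January 2018 is 3.94 months, so 232 + 38.7 is about 271; 270 is used. With z = −ln(HR) × √d / 2:

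| HR | Deaths | z | One-sided p | Two-sided p |
|---|---|---|---|---|
| 0.962 | 232 | 0.295 | 0.384 | 0.768 |
| 0.962 | 250 | 0.306 | 0.380 | 0.759 |
| 0.962 | 270 | 0.318 | 0.375 | 0.750 |

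**4. HR needed for significance at the cutoff.** The documents do not settle the level, so both readings are shown for 232 to 270 deaths.

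| Level applied | Two-sided test | SAP 2.2.1 read literally |
|---|---|---|
| Spending function on observed deaths out of 514 (two-sided 0.0017 to 0.0040) | 0.662 to 0.704 | 0.681 to 0.724 |
| Full 0.05, no efficacy interim having been done | 0.773 to 0.788 | 0.806 to 0.819 |

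An HR of 0.962 is far from all of these.

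**The case against.** The strongest reply is that a careful reader of the whole SAP would reach the two-sided test anyway. SAP 2.2.8.2 labels it the primary analysis, the protocol agrees, SAP 2.2.8.1.1 has its own success rule tied to a two-sided 0.05, and SAP 2.2.1 itself calls the overall level 2-tailed. The boundaries are also printed as hazard ratios, which do not depend on how a p-value is sided. This stands as a limit on the consequence. It does not remove the contradiction, because SAP 2.2.1 is current text and states a decision rule.

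A reader might infer that the boundaries prove the one-sided test itself to be the mistake. They do not. A one-sided test at 0.025 with half the spend gives the same 0.738 and 0.840. The table rules out the literal rule, but it cannot tell whether the slip is a wrong word or a missing statement about halving. SAP 2.2.1 declares benefit in one direction only, so either is plausible.

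A reader might also take one significance threshold for the cutoff analysis as fixed by the documents. SAP 2.2.8.1.1 ties the level to observed deaths, and Protocol 11.8 says the alpha "spent will be adjusted accordingly based on the actual number of events observed". The protocol sentence, however, belongs to an interim that was cancelled. Protocol 11.3 lets the primary OS analysis fall at the cutoff, and SAP 2.2 calls that analysis final. The full 0.05 is therefore an equally available reading.

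**Conclusion.** The point holds. SAP 2.2.1 is wrong as written: it sets a one-sided p-value against un-halved two-tailed levels, in conflict with SAP 2.2.8.2, SAP 2.2.8.1.1 and Protocol 11.3. The sample size and boundaries are correct and need no change.

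It is tempting to conclude that the trial ran at twice its intended error rate. The documents do not support that. The 4.95% requires the literal wording to override the printed boundaries and the other sections, and it belongs to a 308/514-death design that was not carried through.

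No reading alters the conclusion at HR 0.962. The live effect is which OS p-value is reported at the cutoff, about 0.38 or 0.75 to 0.77, and SAP 2.2.8.2 already points to the two-sided one. These values assume 232 to 270 deaths, an HR that stays at 0.962 and the usual normal approximation for the log-rank statistic. The death range rests on the planned accrual of events, not on actual counts, but p hardly moves across it. The correction should be made because the sentence defines success on the primary endpoint and costs almost nothing to repair.

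**What to change.** In SAP 2.2.1, replace one-sided with two-sided. This agrees with SAP 2.2.8.2 and Protocol 11.3 and changes one word.

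Alternatively, keep one-sided and add a sentence stating an overall one-sided level of 0.025 with half the spent alpha at each look (for example 0.0038 instead of 0.0076 at 308 deaths). SAP 2.2.8.2 would then have to say how its two-sided p-value relates to that rule.

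Neither option changes a sample size, boundary or planned analysis.
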